DLQI, CDLQI	
• Mean and change from baseline in Dermatology Life Quality Index (DLQI; age ≥ 16) at each visit through week 24• Percent change from baseline in Dermatology Life Quality Index (DLQI; age ≥ 16) at each visit through week 24• Percent of patients with ≥ 4-point decrease from baseline in DLQI at each visit through week 24• Mean and change from baseline in Children’s Dermatology Life Quality Index (CDLQI; age < 16) at each visit through

	
week 24
 
• Percent change from baseline in Children's Dermatology Life Quality Index (CDLQI; age <16) at each visit through week 24• Percent of patients with ≥ 4-point decrease from baseline in CDLQI at each visit through week 24
HADS	
• Mean and change from baseline in Hospital Anxiety and Depression Scale (HADS) total score, anxiety and depression sub-scores at each visit through week 24• Mean and change from baseline in Hospital Anxiety and Depression Scale (HADS) anxiety and depression sub-scores at each visit through week 24• Percent change from baseline in Hospital Anxiety and Depression Scale (HADS) total score, anxiety and depression sub-scores at each visit through week 24• Percent change from baseline in Hospital Anxiety and Depression Scale (HADS) anxiety and depression sub-scores at each visit through week 24• Percent of patients with Anxiety score < 11 among patients with baseline Anxiety score ≥ 11 at each visit through week 24• Percent of patients with Depression score < 11 among patients with baseline Depression score ≥ 11 at each visit through week 24
AD phenotypic description	
• Percent of each phenotype at baseline• Percent of phenotypes reported as dominant at baseline• For each dominant phenotype, anatomic distribution of lesions at baseline

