Treatment	Question 10	3

Patient Oriented Eczema Measure (POEM)

The POEM is a 7-item, validated questionnaire used in clinical practice and clinical trials to assess disease symptoms in children and adults with atopic eczema ([Charman 2004](#)). The format is patient response to 7 items (dryness, itching, flaking, cracking, sleep loss, bleeding, and weeping) based on symptom frequency during the past week (i.e., 0 = 'no days', 1 = '1 to 2 days', 2 = '3 to 4 days', 3 = '5 to 6' days, and 4 = 'every day'). The total score is the sum of the 7 items which is ranged from 0 to 28; a high score is indicative of a poor QOL. The following POEM banding scores have been established (Charman 2004): 0 to 2 = Clear or almost clear; 3 to 7 = Mild eczema; 8 to 16 = Moderate eczema; 17 to 24 = Severe eczema; 25 to 28 = Very severe eczema. If two or more response options are selected for a question, then the response option with the highest score is recorded. If one question of the seven is left unanswered, then that question is scored as 0 and the scores are summed and expressed as usual out of a maximum of 28. If two or more questions are left unanswered, then the questionnaire is not scored and is set to missing. If two or more response options are ticked for one question, the response option with the highest score should be recorded. Higher score indicates worse condition.

Hospital Anxiety and Depression Scale (HADS)

The HADS is a Likert-scale tool widely used to detect states of anxiety and depression in a general hospital setting ([Bjelland 2002](#)). The 14 items on the questionnaire, assessing how the patient has been feeling in the past week, include 7 items that are related to anxiety (odd numbered questions) and 7 items that are related to depression (even numbered questions). Questions 2, 4, 7, 9, 12, and 14 are scored from 0 (less distress) to 3 (greater distress) according to the content of the item. Questions 1, 3, 5, 6, 8, 10, 11, and 13 are reverse scored from 0 (greater distress) to 3 (less distress).

A person can score between 0 and 21 for each subscale (anxiety and depression). A high score is indicative of a poor state. Scores of 11 or more on either subscale are considered to be a 'definite case' of psychological morbidity, while scores of 8–10 represents 'probable case' and 0–7 'not a case' ([Zigmond 1983](#)).

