For each sub-scale: if one question is missing, the response will be imputed as the mean of the remaining six questions. If more than one question is missing, then the subscale is set to missing. The total score is the sum of the two sub-scores.

HADS will be assessed at time points according to Section [10.2](#).

Skin Pain NRS

Skin pain will be measured using a skin pain NRS that was developed and tested for the study-relevant age group. This is an 11-point scale (0 to 10) in which 0 indicates no pain while 10 indicates worst pain possible. SP NRS can be categorized as: no pain (0), mild (1 to 3), moderate (5 to 6), severe (7 to 9), and very severe (10). The threshold for minimally clinically important difference for SP NRS is between 2.2 to 2.9 ([Silverberg, 2021](#)). The SP NRS will be performed at time points according to Section [10.2](#).

Adult patients will be asked the following question:

- “On a scale of 0 to 10, with 0 being ‘no skin pain or soreness’ and 10 being ‘the worst possible skin pain or soreness’, how would you rate your skin pain or soreness overall, which is on average, during the past 7 days?”

Adolescent patients (≥ 12 to < 18 years at baseline) will be asked the following question:

- “Think about all the areas of your skin with eczema. How would you rate your skin pain at its worst in the past 7 days?”

Patients will be asked to complete this assessment at baseline and then approximately every month throughout the study as indicated in Section [10.2](#).

The baseline Skin Pain NRS score is defined as the prorated average of the Skin Pain scores reported continuously for 7 days right before the baseline visit (i.e. study day -7 to day -1). For post-baseline Skin Pain NRS score, the weekly mean of daily Skin Pain score is calculated as the average of the available reported skin pain score within the week. For example, if there are 3 scores available in a week, the prorated average = $(\text{score1} + \text{score2} + \text{score3})/3$.

Sleep Quality NRS

Study patients will be asked to rate their sleep quality on their past night upon awakening, using the Sleep Quality NRS, ranging from 0 (“Worst possible sleep”) to 10 (“Best possible sleep”). Sleep Quality NRS are to be collected daily including 7 days immediately preceding the baseline visit and then daily during the week before each planned visit.

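### The SAP's HADS rule labels 8 of 14 items with 0 as greater distress and states no recode; programmed as labelled, the anxiety score is net inverted

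*SAP*

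**What the plan says.** SAP section 10.3 assigns the odd-numbered HADS items to anxiety and the even-numbered items to depression, seven each. It then gives the direction of each item in two sentences of the same form:

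- "Questions 2, 4, 7, 9, 12, and 14 are scored from 0 (less distress) to 3 (greater distress)"
- "Questions 1, 3, 5, 6, 8, 10, 11, and 13 are reverse scored from 0 (greater distress) to 3 (less distress)"

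Each subscale is said to run from 0 to 21. On direction, the section says "A high score is indicative of a poor state". On the cut-off, it says "Scores of 11 or more on either subscale are considered to be a" definite case. For missing items within a subscale, "if one question is missing, the response will be imputed as the mean of the remaining six questions". Finally, "The total score is the sum of the two sub-scores".

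SAP section 5.7.2 uses these scores for means, changes and percent changes of the total and both subscales. It also uses them for two shift analyses in participants at 11 or more at baseline: "Percent of patients with Anxiety score < 11 among patients with baseline Anxiety score" at or above 11, and "Percent of patients with Depression score < 11 among patients with baseline Depression score" at or above 11.

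Protocol section 9.2.2.1.8 gives the 0 to 21 range and cut-offs that also rise with severity, but no item-level key.

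**The concern.** The two item lists together cover all 14 items once. If the numbers in both sentences are the scores to be added, eight items add more points when the participant is better, and the subscale cannot run from good to poor as the section says. No 3 - raw step appears in the SAP or the protocol.

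HADS is the study's only dedicated anxiety and depression scale, and a secondary objective concerns those outcomes (Protocol 2.2, SAP 1.2.2). If the sentence is programmed as labelled:

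- changes in anxiety and total score would tend to take the wrong sign;
- depression change would be compressed;
- the groups at 11 or more at baseline would be misclassified.

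The study has a single arm, so no control group would help to expose the error.

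The missing-item rule raises a related question. A mean of the other six items is meaningful only if all six already point the same way, and the SAP does not place any recode before that step.

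**Working it through.** **Inputs (SAP 10.3).** Forward items (0 = less distress): 2, 4, 7, 9, 12, 14. Backward items (0 = greater distress): 1, 3, 5, 6, 8, 10, 11, 13.

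- Anxiety (odd items): backward 1, 3, 5, 11, 13 (5 of 7); forward 7, 9.
- Depression (even items): backward 6, 8, 10 (3 of 7); forward 2, 4, 12, 14.

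**The plan's own figure.** Seven items scored 0 to 3 give 0 to 21, as stated. The stated direction (high = poor) is obtained only if the backward items are flipped.

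**Uniform distress.** Put every item at the same true distress level d (0 to 3). Summed as labelled:

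- anxiety = 2d + 5(3 - d) = 15 - 3d
- depression = 4d + 3(3 - d) = 9 + d
- total = 24 - 2d

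With the flip, each subscale is 7d and the total is 14d.

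| d | Anxiety as labelled | Depression as labelled | Total as labelled | Each subscale, flipped | Total, flipped |
|---|---|---|---|---|---|
| 0 | 15 | 9 | 24 | 0 | 0 |
| 1 | 12 | 10 | 22 | 7 | 14 |
| 2 | 9 | 11 | 20 | 14 | 28 |
| 3 | 6 | 12 | 18 | 21 | 42 |

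A participant with no distress scores 15 on anxiety, above the definite-case cut-off. One with maximum distress scores 6, in the non-case range. Depression keeps its direction but spans 3 points (9 to 12) instead of 21. A one-point improvement on every item gives anxiety +3 (should be -7), depression -1 (should be -7) and total +2 (should be -14).

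**Partial improvement.** There are 2^7 - 1 = 127 ways to improve one or more of the seven items by one point each. The labelled score changes by (backward items improved) - (forward items improved).

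| Subscale | Rises (wrong sign) | Unchanged | Falls |
|---|---|---|---|
| Anxiety | 99 | 20 | 8 |
| Depression | 29 | 34 | 64 |

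**Cut-off at 11.** This weights all 4^7 = 16,384 answer patterns equally, as an illustration and not a forecast. Half of them, 8,192, truly score 11 or more.

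- Anxiety: 2,872 of 8,192 true cases stay at 11 or more (35%), and 5,320 of 8,192 true non-cases enter the group (65%). Correlation of labelled with true score: -0.43.
- Depression: 4,384 of 8,192 stay (54%), and 3,808 of 8,192 enter (46%). Correlation: +0.14.

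Real items are correlated, which strengthens the anxiety inversion. Assume a one-factor normal model with inter-item correlation 0.3 to 0.7 and response thresholds at -0.3, 0.5 and 1.3. The anxiety correlation is then -0.66 to -0.86, and 31% down to 19% of true anxiety cases stay at 11 or more. For depression the correlation is +0.26 to +0.45, and 55% to 64% stay.

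**Order of imputation and recode.** Suppose item 7 is missing and the codes are stored as labelled.

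- d = 0: the mean of the other six codes is (0 + 5 × 3)/6 = 2.5. Anxiety is 15 + 2.5 = 17.5 with no recode, 2.5 if imputed first and recoded afterwards, and 0 if recoded first.
- d = 3: the mean is (3 + 5 × 0)/6 = 0.5. The same three results are 3.5, 18.5 and 21.

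**The case against.** The strongest reply is that 'reverse scored' is itself the recode: the raw options for these eight items run from 0 (greater distress) to 3 (less distress) and are then reversed. Only that reading fits the stated direction and the cut-off in the next paragraph, and it gives correct scores. It may well be what the authors meant. But the sentence attaches the 0 and 3 labels in the same form as the sentence for the forward items, where they clearly are the final scores. It never says that the numbers are raw codes to be flipped. A SAP whose overview promises a formal and detailed description should not leave the programmer to choose.

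There is also no evidence of a wrong result. The CRF coding and the program are not in the documents, and a distress-free participant scoring 15 on anxiety is an anomaly that output review could catch. This stands, so every consequence here is conditional.

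The equal-weight percentages are not realistic for a real scale. That stands too; the uniform-distress table makes the point without them.

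Finally, the text scores the items before it describes imputation, so the natural order is recode, then impute. That is fair, and the 2.5 and 18.5 figures need a programmer who departs from it. The order is still unstated, and clarifying the direction alone would not settle it.

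**Conclusion.** The concern holds. Followed as labelled, the HADS item rule contradicts the section's own score direction and cut-off, and nothing else in the protocol or SAP repairs it. If programmed that way, anxiety and total are net inverted (+3 and +2 for a uniform one-point improvement) and depression is nearly flat (-1). The inversion is net, because anxiety items 7 and 9 still run correctly. If the eight items are in fact flipped before imputation and summation, the results are right and only the wording is at fault.

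The damage is confined to the HADS endpoint and its shift analyses, which are descriptive secondary results. The primary EASI-75 analysis is untouched. The sentence should be corrected, but the point does not threaten the study's main conclusion.

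**What to change.** Replace the item-direction sentences in SAP 10.3 with one rule: every HADS item contributes 0 (least distress) to 3 (greatest distress). If the raw codes for items 1, 3, 5, 6, 8, 10, 11 and 13 are stored with 0 as greatest distress, recode them as 3 - raw before any missing item is imputed and before items are summed. This works under either raw coding and fixes the order of steps.

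Then check the CRF coding and the derivation program against the rule. A simple test is one dummy record with no distress and one with maximum distress on every item, each also run with item 7 missing. Each subscale should return 0 and 21. The cost is one SAP sentence and a program check.

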4.1.2. Secondary Endpoints

Secondary Efficacy Endpoints:

- Proportion of participants with Investigator's Global Assessment (IGA) = 0 to 1 at each visit from baseline through week 24
- Percent change from baseline in EASI at each visit through week 24
- Absolute change from baseline in EASI at each visit through week 24
- Proportion of participants with EASI-50 ($\geq 50\%$ reduction from baseline in EASI) at each visit through week 24
- Proportion of participants with EASI-75 ($\geq 75\%$ reduction from baseline in EASI) at each visit through week 24
- Proportion of participants with EASI-90 ($\geq 90\%$ reduction from baseline in EASI) at each visit through week 24
- Percent change from baseline in total SCORing AD (SCORAD) and SCORAD component scores at each visit through week 24
- Proportion of participants with SCORAD-50 ($\geq 50\%$ reduction in SCORAD from baseline) at each visit through week 24
- Proportion of participants with improvement (reduction) of weekly average of daily Peak Pruritus (PP) NRS ≥ 3 from baseline at each visit through week 24
- Proportion of participants with improvement (reduction) of weekly average of daily PP NRS ≥ 4 from baseline at each visit through week 24
- Percent change from baseline in weekly average of daily PP NRS at each visit through week 24
- Absolute change from baseline in weekly average of daily PP NRS at each visit through week 24
- Change from baseline in percent BSA at each visit through week 24
- Change from baseline in health-related QOL as measured by Dermatology Life Quality Index (DLQI; age ≥ 16), Children's Dermatology Life Quality Index (CDLQI; age < 16) at each visit through week 24
- Change from baseline in Patient Oriented Eczema Measure (POEM) at each visit through week 24

- Change from baseline in Hospital Anxiety and Depression Scale (HADS) at each visit through week 24
- Change from baseline in Skin Pain NRS (SP NRS) at each visit through week 24
- Change from baseline in weekly average Sleep Quality NRS at each visit through week 24
- Proportion of participants with PGID response as No symptoms at each visit through week 24
- Proportion of participants with PGID response as No symptoms or Mild symptoms at each visit through week 24
- Proportion of participants who rate their eczema symptoms in PGIC as “Much better” at each visit through week 24
- Proportion of participants who rate their eczema symptoms in PGIC as “Much better” or “Moderately better” at each visit through week 24

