9.2.2.1.3. Skin Pain NRS (SP NRS)

Skin pain will be assessed using a skin pain NRS with 7-day recall period (Silverberg, 2021). Study participants will be asked to report if they experience any pain of skin over the past week and if yes, rate the severity of pain on a 11-point scale (0 to 10) in which 0 indicates no pain while 10 indicates worst imaginable pain. SP NRS can be categorized as: no pain (0), mild (1 to 3), moderate (5 to 6), severe (7 to 9), and very severe (10). The threshold for minimally clinically important difference for SP NRS is between 2.2 to 2.9 (Silverberg, 2021). The SP NRS will be performed at time points according to [Table 1](#).

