5.7. Analyses of Efficacy Data

The efficacy variables will be summarized for all patients in FAS. The continuous efficacy variables will be summarized using number of patients, mean, SD, median, Q1, Q3, minimum and maximum. Categorical efficacy variables will be summarized using patient counts and percentage. No formal statistical hypothesis testing will be performed. The graph of mean value for continuous variable or proportion for categorical variable by visit will be provided.

Unless otherwise specified, all observed values, regardless of whether data is collected after withdrawal from study treatment will be used for analysis.

Unless otherwise specified, for the categorical efficacy variables, the proportion of patients with each response at each visit will be calculated using the number of patients with a non-missing value at the visit as the denominator.

Subgroup analyses for efficacy

Different subgroups within the FAS population will be defined as below. The analyses will be performed for the primary efficacy variables by:

- Duration of AD (<5 years, \geq 5 years)
- Baseline weight with grouping (\geq 60kg, <60kg for adolescents, <60 kg, \geq 60-<90 kg, \geq 90 kg for adults)
- BMI with grouping (<35, \geq 35-<40, \geq 40)
- Age (\geq 12-<18, \geq 18-<40, \geq 40-<65, \geq 65)
- Sex (Male, Female)
- Race (Black or African American, Asian, Others)
- Fitzpatrick Skin Types phototype (FST 4; FST 5 + 6 [combined])

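### SAP 10.3 gives adults an average and adolescents a worst Skin Pain NRS item, the protocol describes one item for all, and SAP 5.7.2 plans a single unsplit summary

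*SAP*

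**What the plan says.** Protocol 4.1.2 lists the endpoint as "Change from baseline in Skin Pain NRS (SP NRS) at each visit through week 24".

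Protocol 9.2.2.1.3 describes one two-part question for everyone: "Study participants will be asked to report if they experience any pain of skin over the past week and if yes, rate the severity". It makes no distinction by age, or between average and worst pain.

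SAP 10.3, under Skin Pain NRS, prints two questions. Adults are asked "how would you rate your skin pain or soreness overall, which is on average, during the past 7 days". Adolescents, defined as 12 to under 18 years at baseline, are asked "How would you rate your skin pain at its worst in the past 7 days".

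SAP 5.7.2 has one Skin Pain NRS entry, covering the mean, the change and the percent change at each visit through week 24, with no split by age or item. On the population, SAP 5.7 says "The efficacy variables will be summarized for all patients in FAS". The same section lists age 12 to under 18 as a subgroup but introduces the list with "The analyses will be performed for the primary efficacy variables by", and the primary variable is EASI-75. The summary table in SAP 10.1 has a generic Yes under subgroup analysis for continuous efficacy variables.

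**The concern.** The two SAP questions share a name, a 0 to 10 range and a 7-day recall, but they ask for different things. One asks for an average and the other for a peak. The adult question also counts soreness, and the adolescent question does not. On the same construct, a person's worst pain in a week cannot be below their average pain, so the adolescent item would tend to read higher. The soreness wording could offset part of that.

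Nothing in the SAP separates, rescales or bridges the two versions before they enter one summary. DLQI and CDLQI, which also depend on age, have separate rows in SAP 5.7.2. The trial's output is descriptive, so what is at stake is whether a reader can say what the reported skin pain figures measure. Two trials with identical skin pain but different adolescent shares would report different visit means.

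**Working it through.** The plan gives no figure for this point, so there is none to reproduce. The check has a textual part and an illustration.

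**Text**

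- Items: SAP 10.3 has two, assigned by age group; Protocol 9.2.2.1.3 has one. The documents conflict on what is administered.
- Analysis: SAP 5.7.2 has one unsplit entry, applied to the whole FAS by SAP 5.7.
- Subgroups: the specific text in SAP 5.7 limits them to the primary variable. The generic Yes in SAP 10.1 leaves some ambiguity, but even an age-subgroup table would leave the overall row mixed.
- Assignment: the adolescent item goes by age at baseline, so a participant should normally answer the same item throughout. The adult wording has no such qualifier.

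**Illustration, if both items are used**

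Let *w* be the adolescent share, *A* an adolescent's average-pain rating, and *g* the gap (worst minus average), with subscripts 0 for baseline and 24 for week 24. The documents give neither *w* nor *g*. Assume *w* = 0.10 to 0.40, *g*₀ = 1 to 2 points and *g*₂₄ = 0.5 to 1 point. The comparison is with a score in which everyone rates average pain.

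1. Shift in a pooled visit mean = *w* × *g*. At baseline this runs from 0.1 × 1 = 0.1 to 0.4 × 2 = 0.8 points.
2. Shift in the pooled mean change = *w* × (*g*₂₄ − *g*₀):
   - constant gap of 1 point: *w* × (1 − 1) = 0 at every share;
   - smallest narrowing: 0.1 × (0.5 − 1) = −0.05;
   - largest narrowing: 0.4 × (0.5 − 2) = −0.6.

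   A negative value means a larger apparent improvement.
3. Percent change for one adolescent is 100 × (*A*₂₄ − *A*₀)/*A*₀ on the average item and 100 × (*A*₂₄ + *g*₂₄ − *A*₀ − *g*₀)/(*A*₀ + *g*₀) on the worst item. With a constant gap the numerators agree but the divisors differ, so the percent changes differ. They agree if worst pain is a fixed multiple of average pain, but then the absolute changes differ. For a participant whose average pain changes, no non-zero gap leaves both summaries untouched.

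**The case against.** The strongest objection is that the endpoint named in the protocol is change from baseline, a within-patient quantity. Each participant should normally answer one item, so a stable gap drops out. This stands: the 0.1 to 0.8 points describe visit means, not the endpoint. It does not settle the matter, because the gap need not be stable. If worst pain falls to 0, average pain is also 0 and the gap closes.

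A second objection is that two items may never have been administered. The protocol describes one. SAP 10.3 also contains text that does not fit this trial: a cartoon CDLQI for ages 4 to 5 although entry starts at 12, roughly monthly skin pain collection although the schedule includes weeks 2 and 4, and averaging of daily scores for a 7-day-recall question asked at visits. The two-item wording could be more of the same. This also stands, and it is why confirmation comes first. If one item was used for everyone, nothing is mixed and only the SAP wording needs correcting.

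A reader might set the visit-mean shift against the important difference of 2.2 to 2.9 points quoted in both documents and conclude that much of a meaningful effect could be an artefact. The documents do not support that. The threshold concerns a difference, whereas the shift is in a cross-sectional mean built on assumed inputs. SAP 5.7.2 also plans no Skin Pain analysis that uses the threshold.

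**Conclusion.** The concern holds conditionally. The conflict between Protocol 9.2.2.1.3 and SAP 10.3 is on the page and needs resolving in any case. If both items were administered, the planned visit means and percent change combine two different measures and vary with the adolescent share. Under the assumed ranges, the pooled baseline mean moves by 0.1 to 0.8 points. The effect on mean change runs from none with a constant gap to 0.6 points in the most extreme assumed case; its actual size cannot be derived from the documents.

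A reader might infer that the secondary endpoint itself is invalid, or that the overall summary must be removed. Neither follows. Change is within patient, and the protocol endpoint is not defined by item version, so an overall row may stay if it is labelled. The study does no hypothesis testing, and the primary endpoint, error rates and sample size are not touched. The change is worth making because it costs little and lets a named secondary endpoint be interpreted.

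**What to change.** 1. Confirm from the questionnaires in use which Skin Pain item each age group received, and reconcile Protocol 9.2.2.1.3 with SAP 10.3.
2. If one item was used for everyone, correct SAP 10.3 and leave SAP 5.7.2 unchanged on this point.
3. If two were used, add separate Skin Pain NRS rows in SAP 5.7.2 for adults (average item) and adolescents (worst item), with both groups defined by age at baseline. Name these as the rows used for interpretation, and footnote any overall row as combining two item versions.

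The cost is SAP wording and one table split, with no new data. The drawback is a small adolescent row: at the assumed shares and full enrolment of 120, it would hold 0.10 × 120 = 12 to 0.40 × 120 = 48 participants before any missing data. The separate CDLQI row for those under 16 already carries a similar limitation.

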10. Assessments/procedures should be conducted in the following order: Patient-Reported Outcomes (PROs), investigator assessments, safety and laboratory assessments, administration of study drug. Clinical sites will check participant data collected on the diary. Topical emollient (moisturizer) should be applied twice daily, as per physician's recommendation starting at the screening visit. Participants should continue to apply moisturizers throughout the study. However, to allow adequate assessment of skin dryness, moisturizers should not be applied on the day of the study visit.

11. These assessments are to be completed by study participants in their diaries: Peak Pruritus NRS will be conducted daily starting 7 days prior to baseline. Sleep Quality NRS is to be collected daily for 7 days immediately preceding the baseline visit and all subsequent visits.
12. CDLQI for participants <16 years of age, DLQI for participants ≥ 16 years of age.
13. AD phenotypic description (primary morphologies, and distribution) includes the following: Localized AD, Flexural AD, Extensor AD, Nummular AD, AD with prurigo nodules, Follicular AD, Papular AD, Lichenoid AD, and Psoriasiform AD
14. A photography substudy will be performed at a subset of study sites. Site training will be provided. Participant/parents or legal guardians who agree to participate in the substudy will be required to sign a separate substudy informed consent/assent form for use of photographs for educational/marketing purposes before the procedure is performed.
15. A colorimetry substudy will be performed at a subset of study sites. Site training will be provided. Participant/Parents or legal guardians who agree to participate in the substudy will be required to sign a separate substudy informed consent/assent form before the measurements are performed.
16. An OCT substudy with additional non-invasive in vivo imaging including line field confocal OCT and/or reflectance confocal microscopy at the discretion of the investigator will be performed at a single study site. Participant/Parents or legal guardians who agree to participate in the substudy will be required to sign a separate substudy informed consent/assent form before the procedure is performed.
17. Any participant who experiences an AESI related to an eye disorder will be referred to an ophthalmologist if deemed necessary by the investigator.

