12.1.2. Electronic Systems

Electronic systems that may be used to process and/or collect data in this study will include the following:

- IVRS/IWRS system – study drug supply
- EDC system – data capture – Medidata RAVE
- Statistical Analysis System (SAS) – statistical review and analysis
- Sanofi-Genzyme Pharmacovigilance safety database
- AWARE, Business Objects XI – pharmacovigilance activities (Sanofi)
- Digital archive system for photographic and video images
- Electronic diary - collection of PP NRS and Sleep Quality NRS

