6.1. Definition of Baseline for Efficacy/Safety Variables

Unless otherwise specified, the baseline assessment for all measurements will be the latest available valid measurement taken prior to the first administration of study drug in the current study. The following rules specify the determination by both date/time information:

1. For the AE, both date and time of the measurement will be used to determine baseline by comparing with the first injection date and time.
2. For other data except AE, only date of the measurement will be used to determine baseline by comparing with the first injection date if date is available. If no first injection date record available, baseline visit data without available date will be used. If there is no baseline visit, screening visit data without available date will be used.

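### SAP 10.3: the Skin Pain NRS baseline window contains no scheduled score, and the HADS text codes 8 of 14 items against the scale's stated direction

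*SAP*

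**What the plan says.** **Skin Pain NRS.** Protocol 4.1.2 lists as a secondary endpoint "Change from baseline in Skin Pain NRS (SP NRS) at each visit through week 24". Protocol 9.2.2.1.3 states: "Skin pain will be assessed using a skin pain NRS with 7-day recall period". Table 1 of the Protocol and its copy in SAP 10.2 mark the item at the baseline visit (day 1), at weeks 2, 4, 8, 12, 16, 20 and 24, and at early termination. Screening and the week-1 phone visit are blank. The diary entry in Protocol 12.1.2 reads "Electronic diary - collection of PP NRS and Sleep Quality NRS". SAP 10.3 first says the item is completed at baseline and then roughly monthly. It then gives baseline this definition: "prorated average of the Skin Pain scores reported continuously for 7 days right before the baseline visit (i.e. study day -7 to day -1"). It describes post-baseline values as weekly means of daily scores. The default in SAP 6.1 is: "Unless otherwise specified, the baseline assessment for all measurements will be the latest available valid measurement taken prior to the first administration".

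**HADS.** Protocol 4.1.2 also lists "Change from baseline in Hospital Anxiety and Depression Scale (HADS) at each visit through week 24". SAP 10.3 assigns odd items to anxiety and even items to depression. It scores items 2, 4, 7, 9, 12 and 14 upward with distress and then says: "Questions 1, 3, 5, 6, 8, 10, 11, and 13 are reverse scored from 0 (greater distress) to 3 (less distress"). The same text gives each subscale a range of 0 to 21, says higher is worse, and calls 11 or more a definite case. One missing item in a subscale is replaced by the average of the other six. SAP 5.7.2 reports, for each subscale, the proportion below 11 among participants at 11 or more at baseline.

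**Sleep Quality NRS.** SAP 10.3 puts its baseline at days −7 to −1; the diary windows in SAP 6.3 put it at days −6 to 1.

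**The concern.** These are scoring rules that a programmer is meant to follow as written.

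- The Skin Pain rule averages scores over a week in which none is scheduled. Change and percent change from baseline would then be empty.
- The HADS rule adds items that run in opposite directions, and the SAP still interprets the sum as though higher were worse. That can reverse the sign of a participant's change and put the wrong people into the responder denominator.

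HADS is the named anxiety and depression endpoint, so it carries the mental-health part of a secondary objective. The two errors also differ in visibility. An empty Skin Pain baseline would be noticed at once. Wrongly summed HADS subscales still lie between 0 and 21, so a range check would pass them.

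**Working it through.** **Skin Pain window**

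- Scheduled days (Table 1): 1, 15, 29, 57, 85, 113, 141, 169. Early termination visits come after baseline.
- Baseline window (SAP 10.3): days −7 to −1.
- Scheduled days inside the window: 0. The screening visit may fall there, but the item is not marked at screening.
- The SAP 6.1 default would select the day-1 score, but it gives way wherever the SAP specifies otherwise, and 10.3 does.
- The day-1 score is pre-dose, by footnote 10 to Protocol Table 1: "Assessments/procedures should be conducted in the following order: Patient-Reported Outcomes (PROs), investigator assessments, safety and laboratory assessments, administration of study drug".
- The post-baseline averaging text is also wrong for this item, but harmless: the mean of one score is that score.

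**HADS direction**

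The plan's own range reproduces: 7 items × 3 = 21 per subscale. The two item lists cover items 1 to 14 without overlap (6 + 8 = 14).

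- Anxiety (odd items): 1, 3, 5, 11 and 13 are reversed (5 of 7); 7 and 9 are not.
- Depression (even items): 6, 8 and 10 are reversed (3 of 7); 2, 4, 12 and 14 are not.

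Let x be the distress on an item, from 0 (least) to 3 (greatest). The text as written gives:

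- anxiety = 15 − (sum of x over the 5 reversed items) + (sum of x over the other 2)
- depression = 9 − (sum of x over the 3 reversed items) + (sum of x over the other 4)

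The anxiety score therefore rises whenever the total improvement on its five reversed items exceeds that on items 7 and 9. For illustration, set every item to the same level k:

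- anxiety = 5(3 − k) + 2k = 15 − 3k
- depression = 3(3 − k) + 4k = 9 + k
- total = 24 − 2k
- intended: 7k, 7k and 14k

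| k | Each subscale, intended | Anxiety, as written | Depression, as written | Total, intended | Total, as written |
|---|---|---|---|---|---|
| 0 | 0 | 15 | 9 | 0 | 24 |
| 1 | 7 | 12 | 10 | 14 | 22 |
| 2 | 14 | 9 | 11 | 28 | 20 |
| 3 | 21 | 6 | 12 | 42 | 18 |

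- Improvement from k = 2 to k = 1 should take anxiety from 14 to 7 and the total from 28 to 14. As written, anxiety goes from 9 to 12 and the total from 20 to 22.
- The anxiety responder denominator (baseline 11 or more) admits k = 0 and 1 and excludes k = 2 and 3, the reverse of what is meant.
- Depression keeps its direction in this illustration, but each step in k moves it by 1 point instead of 7.
- Missing item: with item 7 missing and no distress (k = 0), the other six anxiety items sum to 5 × 3 + 0 = 15. The imputed value is 15/6 = 2.5 and the subscale is 17.5 instead of 0.

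**Sleep Quality (minor)**

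- There is no study day 0, so days −7 to −1 and −6 to 1 share 6 of 7 days.
- The week-24 diary window in SAP 6.3 runs from 2 + 7 × 23 = 163 to 8 + 7 × 23 = 169.
- If the diary week precedes the planned date (day 169), it covers days 162 to 168, and 6 of 7 fall in the window.
- If it precedes the actual visit, the ±7-day visit allowance matters. A visit on day 162 gives diary days 155 to 161 (0 in the window); one on day 176 gives days 169 to 175 (1 in the window).

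**The case against.** The best defence is that the intended rules are evident from the rest of the plan.

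- For Skin Pain, SAP 4.1 and the analysis table in SAP 5.7.2 attach weekly averages to Peak Pruritus but not to this item. SAP 6.3 places the Baseline visit on day 1, and 10.3 itself says the item is completed at baseline. The averaging paragraph closely resembles the Sleep Quality text, so a carry-over is likely, though that is inference. A programmer would not accept change scores missing for everyone.
- For HADS, the stated direction and the cut-offs (with similar ones in Protocol 9.2.2.1.8) fix what a high score means. The reverse-scoring sentence may describe the raw order of the response options. The table above needs literal summing and an artificial participant with equal distress on all items.
- The study is descriptive and single-arm, with no hypothesis tests, and these are two of many secondary endpoints.

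Most of this stands as evidence of intent, and it points to the correction. It does not make the written rules right. The SAP states no recoding step for HADS, and the ambiguity cuts both ways: if the database already holds corrected codes, applying the sentence would reverse them wrongly. The equal-distress participant is only an illustration, but the sign problem follows from the item lists and does not depend on it.

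On Sleep Quality, Protocol 9.2.2.1.2 and SAP 10.3 refer to planned visits, which favours the reading with 6 of 7 days. Footnote 11 to Protocol Table 1 leaves out that word, so the point stays minor but open.

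**Conclusion.** The concern holds. As written, the Skin Pain NRS baseline draws on 0 scheduled scores, although a usable pre-dose day-1 score exists. The HADS text codes 8 of 14 items (5 of 7 anxiety, 3 of 7 depression) against the scale's own direction.

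The Skin Pain result assumes that participants follow the schedule, with the first dose on the day of the baseline visit; an unscheduled earlier score could fall in the window. The HADS figures assume the text is applied literally to every item and, for the table, equal distress on all items. They show the contradiction and do not estimate a likely error.

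The primary EASI-75 analysis is unaffected, and both endpoints can be recovered from the data as collected. The Sleep Quality mismatch is secondary. This should be corrected before programming.

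**What to change.** - **Skin Pain NRS (SAP 10.3):** define baseline as the single score at the baseline visit (day 1), completed before the first dose, and each post-baseline value as the score at that visit. Delete the daily and weekly averaging text for this item.
- **HADS (SAP 10.3):** state that all 14 items are coded from 0 (least distress) to 3 (greatest distress) before any summing and before the missing-item rule is applied. Check how the database stores the items so that they are recoded only once, if at all.
- **Sleep Quality NRS (SAP 6.3 and 10.3):** use one baseline window in both sections, and state whether diary weeks follow the planned or the actual visit date.

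The cost is a few sentences in SAP 6.3 and 10.3 and one check of the stored HADS items. No new data are needed.
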